9.2.1 Consenting process

Informed consent is not limited to the signing of the consent form; it also includes all written or verbal study information site staff discuss with the patient, before and during the trial. Once an eligible participant is identified, the study team will coordinate a consent conference with the patient or LAR. This can be done in person or via phone/video conference. The patient or LAR will have a copy of the consent form to review during the conference. The patient or LAR will be given ample time to review the consent and ask questions.

When a previously incapacitated patient regains capacity to consent, the study team will schedule a follow up consent conference with the participant and document their willingness to continue participating in the study.

The consenting process for each site will be documented in the individual “Participating Site Application”. Participating sites (initial sites listed in Appendix H) may use resources available to their site to conduct eConsent if it meets FDA 21 CFR Part 11 compliance. A template Prescreening consent (for participants where leftover blood sample is not available) and Main consent template will be given to the participating sites to modify.

9.2.2 Consent form

The informed consent form documents that a prospective patient or their agent (1) understands the potential risks, benefits, and alternatives to participation, and (2) is willing to participate in a study.

This study will conduct multi-site research under the regulatory approval of a Single Institutional Review Board (sIRB) in accordance with the NIH Policy on the Use of a Single Institutional Review Board for Multi-Site Research. The Fred Hutchinson Cancer Center IRB (FWA00001920) will serve as the sIRB of record that is responsible for overseeing the conduct of this study. All collaborating sites (initial sites listed in Appendix H) have agreed to rely on the sIRB and any sites added after study initiation will also be required to rely on the sIRB. The Principal Investigator (PI) will disseminate the proposed informed consent to all participating sites and will submit these materials to the sIRB for review and approval. Any subsequent changes will be distributed to sites and submitted to the sIRB as a modification to be approved prior to implementation. The consent form(s) must be developed in accordance with local IRB/IEC requirements and the principles of informed consent as described in Title 45, Code of Federal Regulations (CFR) Part 46 and Title 21 CFR, Part 50, and in the International Conference on Harmonisation (ICH) E6: Good Clinical Practice: Consolidated Guidance 4.8. It must be approved by all responsible ethical review bodies before any subjects can be deemed to have consented for the study.

9.3 Screening procedures

Screening procedures are done to determine eligibility and to provide a baseline for comparison of data. Baseline data are obtained during screening. All inclusion and exclusion criteria must be assessed within 120 hours before randomization. Importantly, the patient can only be randomized once these test results are available.

Before randomization, the following procedures are performed:

- Clinical laboratory tests as defined in the inclusion and exclusion criteria, including:
 - Serum or urine pregnancy test—the results of this must be negative before proceeding, since ganciclovir is suspected to be teratogenic.
 - CMV serology by lateral flow assay (LFA) or gold standard test. See **Figure 9-1 and Section 9.3.1** for the specific algorithm by which the LFA and confirmatory gold standard test will be used for CMV serology.
 - Leftover serum (preferred) or plasma may be used if available.
 - If leftover material is not available, a small amount of extra blood (0.5-1.5 ml) should be obtained after prescreening consent is administered to permit such testing. Prescreening consent may be obtained verbally or as written consent, as permitted per IRB guidelines.
 - After lateral flow testing is obtained, a portion of the same sample should be sent to a CLIA-approved lab for testing.
 - Absolute neutrophil count/total white blood cell counts

- Collection of medical history
- Collection of samples for CMV PCR in plasma and endotracheal aspirates as well as for storage for subsequent CMV immunity testing, genomic analysis, and ancillary studies
- Assessment of select concomitant medications: steroids, immunosuppressive medications and antivirals
- Net fluid balance at ICU admission
- Obtaining of patient demographics in compliance with the NIH Policy on Reporting Race and Ethnicity Data: Subjects in Clinical Research, Aug. 8, 2001. Available at <http://grants.nih.gov/grants/guide/notice-files/NOT-OD-01-053.html>

9.3.1 CMV Serology Screening Procedures

CMV serology test results (for rapid CMV serology [LFA] and CLIA test) are reported as a qualitative “Positive” or “Negative”, and very rarely “Indeterminate.”

Randomization can occur in the follow instances:

- If the Rapid CMV Serology (LFA) comes back positive, randomization can occur prior to the CLIA test.
- If the Rapid CMV Serology (LFA) comes back indeterminate or negative, and then the CLIA test comes back as positive, randomization can occur.
- If sites do not perform a Rapid CMV Serology (LFA) test, and the CLIA test comes back as positive, randomization can occur.

If Rapid CMV Serology (LFA) testing is done, a site progresses to the CLIA test as follows:

[figure not shown]
- Regardless of whether the Rapid CMV Serology (LFA) comes back positive, indeterminate, or negative, progress to the CLIA test (using part of the same sample used for the rapid test, as described in section 9.3 above).
- CLIA test result must be recorded as either positive or negative; an indeterminate CLIA test result should be recorded as negative.

Rapid CMV Serology (LFA) is NOT required to progress to CLIA testing:

- Sites can perform only CLIA testing and randomize with a single positive test result.

Discordant results (between the LFA and CLIA test) that lead to administration of study drug will be tracked and reviewed regularly by the Safety and Protocol Adherence Review Team (Section 14.3).

Figure 9-1. Flow diagram of serologic assessment strategy for inclusion using LFA with confirmation via standard serologic assay. PPV and NPV for LFA are calculated based on 60% seroprevalence, using QNow UV Flashlight reader as is planned for this study.

9.4 Patient Registration

Participating sites can verify a patient's consent and eligibility and register the patient into the study. DCC will provide patient accrual reports. Randomization will be through MediData's Balance system, 24/7, with a backup system in place.

9.5 Randomization procedure

Randomization will occur after assessment of positive CMV serostatus as detailed in **Section 9.3.1**, and negative pregnancy test. Randomization and first dose of study drug should occur as close to each other as possible. Randomization and first dose of drug **must** occur within 120 hours of hospital admission **and** on the same calendar day. Patients who are randomized but in whom the need for respiratory support ends, who die, are outside of the 120 hour window, or have consent withdrawn before receiving first dose of study drug should not receive their first dose of drug and are withdrawn from the study (see Section 7.5).

The randomization sequence will be uploaded by SCHARP into the MediData's Randomization and Trial Supply Management (RTSM) system and provided to each site through MediData. This

system automatically notifies the site pharmacist of the treatment assignment. The randomization will be block-randomized by site. At each institution, the pharmacist with primary responsibility for drug dispensing is charged with maintaining the security of the randomization list. Patients will be stratified at the time of randomization according to treatment center.

When the patient is randomized, the following information is required by NIH reporting guidelines: date of birth, race/ethnicity, and gender. For the purpose of this study, each patient will be assigned a study number, which will be used for all communications with outside institutions to assure confidentiality.

A CLIA-certified standard serologic assay will be used to confirm CMV positivity, but patients with a positive rapid test result may be randomized prior to the return of the CLIA test results (see **Section 9.3.1**).

Randomization will continue until the target accrual number for participants in the primary analysis are met. The primary analysis population will be all patients randomized who receive at least one dose of the assigned study product.

9.6 First dose of study drug

Study day 1 is defined as the first calendar day on which the patient is randomized and the first dose of study drug is administered. All subsequent study days will start accordingly. At baseline, but before administration of study drug, the following procedures will need to be performed:

- Blood: Creatinine, CMV cell-mediated immunity, platelets, CMV plasma PCR, CBC w/differential, research samples.
- Endotracheal aspirate (ETA). If patient is intubated, collect an ETA specimen at baseline (\pm 1 day) and twice weekly, at the time that this procedure is routinely performed by respiratory therapy. Specimens will be labeled and stored frozen for subsequent CMV PCR analysis at the coordinating lab at Fred Hutch.
- Clinical Assessments: Apache III, SOFA, COMS survey (see Section 9.10), static respiratory compliance, ventilator parameters, assessment of select concomitant medications (steroids, immunosuppressive medications, neuromuscular blockers, and antivirals), use of ECMO and prone positioning, and bilateral vs. unilateral infiltrates on chest radiograph. See Section 9.11 for details on these assessments.

9.7 Intervention (Study drug administration)

Patients will be randomized in a 1:1 ratio to receive either ganciclovir or placebo. Study drug delivery should begin as soon after randomization as possible; it must occur on the same day as randomization and within 120 hours of hospitalization. The first day of study drug is considered Day 1 of this study.

- Study drug will be administered for a maximum of 28 days. For the initial 5 days of study treatment, the dose will be ganciclovir 5mg/kg or Placebo IV q 12hr.
- If the patient is discharged from the hospital prior to day 28 or when intravenous access is removed, the patient will stop receiving study drug.
- After 5 days, the dose will be reduced to ganciclovir 5mg/kg or placebo IV once daily.
- Ganciclovir doses must be adjusted according to renal function as per package insert.

- Biopsy-proven CMV disease (eg colitis/esophagitis) can occur very infrequently in very sick but immunocompetent patients. In such circumstances, one of the PIs should be contacted and it should be specified that study medication (which could be GCV or placebo) is to be held, and open-label GCV administered. This would likely lead to unblinding since it would be presumed that breakthrough CMV disease is very unlikely to occur while receiving IV GCV at prophylactic doses (those used in this study after day 5). See section 9.15 for more information on unblinding procedures.

9.8 Co-interventions

All patients will receive standard intensive care unit care, which includes respiratory support and ventilator management (standardized lung protective ventilation [Appendix D] and fluid management [Appendix E] protocols will be used at all sites for mechanically ventilated patients, and Appendix I provides recommended approaches for high-flow nasal cannula oxygen and non-invasive ventilation), antimicrobial therapy, blood glucose control, and ICU sedation. Many of these co-interventions occur under local protocols used as a part of routine clinical care at the clinical sites (initial sites listed in Appendix H).

9.9 Specimen collection

Patients will undergo serial blood draws at study entry (± 1 day of randomization) and plasma CMV PCR samples every seventh day while on study. Not more than 200 mL of blood will be collected over the initial 28 days of the study. A substudy of patients will have plasma collected every four days while hospitalized.

Collect an ETA specimen at baseline (± 1 day), and also every fourth day (± 2 days) at intensified monitoring sites, while the patient is intubated, at the time this procedure is routinely performed by respiratory therapy. BAL fluid (from a standard or "mini" bronchoscopy) may be collected in the place of ETA. Specimen will be collected, labeled, and stored frozen for subsequent CMV PCR analysis at the coordinating center lab ([name] Lab at Fred Hutch).

After hospital discharge, patients will not be followed daily, but they will be contacted at Day 28 (± 4 days) if not hospitalized, and Day 180 for a telephone follow-up to ascertain reportable adverse events, vital status, pregnancy status (at Day 28), and pregnancy within 30 days of study drug (at Day 180).

9.10 Patient-Centered Outcomes Survey (COMS)

Patients will complete a survey at baseline and at 6 months (NHLBI COMS), by previously agreed-upon communication preference. The purpose of this survey is to compare functional assessment and well-being (patient-centered outcomes), at 6 months between ganciclovir and placebo recipients.

At baseline, patients or LARs will complete the Katz Index of Independence in Activities of Daily Living (ADL) and Lawton – Brody Instrumental Activities of Daily Living Scale (IADL), which will take approximately 4 minutes to complete.

At 6 months, patients will be asked to again complete the ADL, IADL, and to complete the Hospital Anxiety and Depression Scale (HADS), EQ-5D-5L, and Impact of Events Scale – Revised (IESR). The survey will take approximately 15 minutes to complete.

9.11 Post-Enrollment Procedures

See the schedule of procedures for specific time points (including permissible windows) in Appendix A. Duration of participation in the study by individual patients will be 180 days.

- Blood:
 - Creatinine, Platelets, CBC w/differential - Days 4, 7, 11, 14, 18, 21, 25, 28 (all \pm 1 day); can be obtained from clinical testing results if available
 - CMV PCR (all \pm 1 day):
 - At intensified monitoring sites: Days 4, 7, 11, 14, 18, 21, 25, 28
 - At all sites: 7, 14, 21, 28 at all sites
- ETA: At intensified monitoring sites, CMV PCR, twice weekly (\pm 2 days) while intubated.
- Clinical Assessments:
 - SOFA score daily on Days 1-7, then twice weekly (Day 11, 14, 18, 21, 25, 28) through day 28 if still in the ICU
 - Vital status (collected as ICU and hospital mortality at discharge, and 180-day mortality)
 - Assessment of concomitant antiviral medications daily on Days 1-7, then twice weekly through day 28
 - Ventilator parameters and static respiratory compliance (daily if mechanically ventilated), NIV parameters, and HFNC parameters daily.
 - Net fluid balance at ICU admission and net cumulative fluid balance until ICU discharge
 - Use at any point during study (and if used, duration/number/dose) of ECMO, prone positioning, steroids, neuromuscular blockers; collected at hospital discharge
 - Occurrence of bacteremia and fungemia; collected at discharge
 - Use of antibacterials or antifungals in the event of ventilator-associated pneumonia or nosocomial pneumonia (defined as sputum, BAL or ETA culture with new pathogen associated with new antibiotic +/-48 hours from culture). Any antibacterial used to treat bacteremia or antifungal used to treat fungemia should be reported.
 - Apache III at baseline only
 - COMS survey (see Section 9.10) at Day 180 (\pm 6 weeks)
 - Bilateral versus unilateral infiltrates on chest radiograph: To be assessed as close as possible to, but not prior to, randomization. Chest radiograph at admission is acceptable if it is the only one available. If the word "bilateral" is not on the report of the chest radiograph, then the coordinator will ask the site PI to assign unilateral, bilateral, or "no infiltrates" to the patient's chest radiograph. If the word bilateral is in the report, then the coordinator will assign bilateral.
- For women of childbearing potential, a serum pregnancy test will be performed at day 7 or at the time of hospital discharge if discharged before study day 7.
- In patients discharged from the hospital before day 28, a follow-up call will be completed on day 28 (\pm 4 days) to assess reportable adverse events, vital status, and pregnancy. Vital

status and pregnancy within 30 days of last dose of study drug will also be assessed during the day 180 follow-up phone call.

- Because ganciclovir carries a black box warning for tumors in lab animals, at the Day 180 follow-up call subjects will be asked if there is any known new development of a malignant tumor. If a new tumor is reported, records will be requested from the primary care physician or hospital.

Follow up for this study population has been historically difficult. Despite effort by sites to obtain all study specimens, it is expected that there may be missed blood draws after discharge from the hospital. Because these missed labs are expected, they will not be considered to be unanticipated problems or protocol violations. In the event a patient cannot be reached for the 180 Day follow up, survival data may be determined through death registry records.

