4.1 Rationale for study population

4.1.1 Definitions of sepsis, acute respiratory failure, and respiratory support

The study population is sepsis-associated acute respiratory failure.

Sepsis will be defined according to the recent Sepsis-3 consensus definition (outlined briefly below and in more detail in Appendix G) [72]:

- Infection suspected or confirmed by the treating physician and
- Organ dysfunction measured as an acute change in total SOFA score ≥ 2 points after the infection (baseline SOFA score assumed 0 unless known pre-existing organ dysfunction).

Acute respiratory failure will be defined as the concurrent presence of :

- $\text{PaO}_2/\text{FiO}_2 \leq 300\text{mmHg}$ if PaO_2 is available. If PaO_2 is not available, the SpO_2 must be $\leq 96\%$ on any FiO_2 setting $\geq 40\%$,*

AND

- New, or if no prior imaging, presumed new unilateral or bilateral infiltrates on chest imaging occurring in the setting of sepsis from any source,

AND

- Requiring **respiratory support for respiratory failure**.

For this study, **respiratory support** includes high flow nasal cannula oxygen with a flow rate $\geq 30 \text{ L/min}$, non-invasive ventilation by mask or helmet with any mode including pressure support, CPAP, or bi-level CPAP (BiPAP) with the equivalent of positive end-expiratory pressure (PEEP) $\geq 5 \text{ cmH}_2\text{O}$, or invasive mechanical ventilation via endotracheal tube or tracheostomy with PEEP $\geq 5 \text{ cmH}_2\text{O}$. It does not include respiratory support for sleep apnea or conditions other than acute respiratory failure.

- * Although FiO_2 is difficult to estimate at lower flow HFNC oxygen, for purposes of this study, the set FiO_2 during HFNC oxygen therapy will be used as the study FiO_2

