6.2.2 Secondary endpoints

[figure not shown]
For the quantitative secondary endpoints (including a key secondary endpoint of VFDs or ventilator-free days), the same method as described in the analysis plan for the primary endpoint will be used. For time to event endpoints including CMV reactivation at given thresholds, the Kaplan-Meier method will be used to estimate the probability of not experiencing CMV reactivation by Day 28 for each group. A 95% confidence interval about the group difference in event rates will be computed using the two Kaplan-Meier estimates and the two Greenwood variance estimates. Based on these estimates, a Z-statistic will be used for testing for difference in the group event rates. The multiple testing problem will be handled using a Bonferroni correction, whenever such situations arise. Additionally, multivariate models will be built for the primary endpoint (RSFD) as well as other secondary endpoints, after adjusting for baseline subject characteristics and risk factors for CMV reactivation, using generalized linear models or the semiparametric efficient and robust method of Davidian et al. [89, 90]. The list of baseline characteristics to be considered for adjustment are those listed in (1) under the Exploratory Objectives/Endpoints (Section 5.3). We will repeat the above analyses in several subgroups (separately) as well, including those who are PCR negative at baseline, as well as those that have septic shock, pneumonia, unilateral infiltrates, or lymphopenia at the time of randomization, and by age and sex. In addition, we will repeat the above analyses in the following subgroups as follows: (1) VFDs in those on invasive mechanical ventilation at randomization; (2) RSFDs in those on invasive mechanical ventilation at randomization; (3) RSFDs in those on NIV/high flow at randomization; (4) Intubation after enrollment in those on NIV/HFNC at randomization (i.e. does ganciclovir affect the need for intubation in this subgroup?); (5) RSFDs according to COVID-19 status at randomization; and (6) CMV detection in plasma by day 28 (28 (>0 IU/mL, >1000 IU/mL) in those with invasive mechanical ventilation vs. NIV/high flow at randomization.

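### Infiltrate laterality can be read from a film taken after the first dose and is coded by a word match, so the planned unilateral-infiltrate subgroup can be post-treatment and can lose true unilateral cases

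*Combined protocol and SAP*

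**What the plan says.** Five parts of the protocol bear on this variable.

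- **Eligibility (4.1.1).** A participant needs new or presumed new "unilateral or bilateral infiltrates on chest imaging occurring in the setting of sepsis". Either pattern qualifies. The section explains that the bilateral requirement was deliberately removed.
- **Baseline procedures (9.6).** The list opens with "At baseline, but before administration of study drug, the following procedures will need to be performed", and its clinical assessments end with "and bilateral vs. unilateral infiltrates on chest radiograph". It refers to 9.11 for details.
- **Post-enrollment procedures (9.11), timing.** The item is "To be assessed as close as possible to, but not prior to, randomization". One exception follows: "Chest radiograph at admission is acceptable if it is the only one available".
- **Post-enrollment procedures (9.11), coding.** If the word 'bilateral' is absent from the report, "then the coordinator will ask the site PI to assign unilateral, bilateral, or" no infiltrates. If the word is present, the site PI is not asked: "If the word bilateral is in the report, then the coordinator will assign bilateral".
- **Use (6.2.2).** Analyses are to be repeated in several subgroups, including "those that have septic shock, pneumonia, unilateral infiltrates, or lymphopenia at the time of randomization".

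The subgroup list in SAP Section 11 does not include laterality. SAP Section 12, which records changes from the protocol, does not say that it was dropped.

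**The concern.** A subgroup described as of randomization should rest on information that existed at randomization. Every eligible participant has such information, because infiltrates on chest imaging are an entry requirement and Section 9.3 has the criteria assessed before randomization. Where a later film exists, 9.11 passes over the earlier image in its favour. Once a film postdates the first dose, disease course and possibly treatment can influence who is labelled unilateral, and a comparison of arms within that label is no longer protected by randomization.

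The coding rule is a separate problem. It looks for a word and not for a finding. A report of one-sided consolidation with bilateral pleural effusions, or a statement that there are no bilateral opacities, is coded bilateral with no second look. The error can run only one way: true unilateral cases move to bilateral.

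At stake is the readability of one planned subgroup analysis. It is the subgroup closest to the decision in 4.1.1 to admit patients without bilateral opacities, although the protocol does not state that as its purpose.

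**Working it through.** **Timing: the rules side by side**

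1. 9.11 sets an earliest time (randomization), asks for closeness, and sets no latest time. It sends the reader to Appendix A for permissible windows, but Appendix A has no chest-radiograph row.
2. 9.6 sets a latest time: before study drug.
3. Sections 9.5 and 9.7 put randomization and first dose on the same calendar day, as close together as possible.
4. Applied together, 1 and 2 leave only the gap between randomization and first dose. A film in that gap cannot be affected by treatment.
5. Applied alone, 9.11 accepts a film from any later day.
6. The exception covers an admission film that is the only film. Read literally, it gives no rule for a participant who has an admission film and a second film before randomization, but none after.

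The two sections therefore do not settle which film defines the variable, and one permitted reading makes it post-treatment.

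**Coding: an illustration of size**

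The plan gives no figure for this subgroup, so there is none to reproduce. As a check on the inputs borrowed from the protocol's Section 6.1.1 (difference 2.74 days, SD 9.4, two-sided 5%, 85% power), the t-test calculation gives 212.3, rounded up to 213 per arm. This matches the stated 213.

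Inputs:
- Planned N = 500 (protocol Section 7.1).
- Unilateral share 33%. This is an assumption: the complement of the 67% meeting ARDS criteria in 4.1.1. 500 × 0.33 = 165 unilateral and 335 bilateral.
- Miscoding rate m, the share of unilateral cases whose report contains the word in another sense. This is also an assumption, varied from 0 to 30%.
- All other cases are taken as correctly labelled, with equal arms within the subgroup.

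Formulas:
- Labelled unilateral: u = 165 × (1 − m).
- Truly unilateral share of the labelled bilateral group: f = 165m / (335 + 165m).
- Observed difference in effect between the labelled groups: (1 − f) × the true difference. This assumes that miscoded cases respond like other unilateral cases.
- Power for 2.74 days in the labelled unilateral group: Φ(2.74 / (9.4 × √(2/(u/2))) − 1.96).

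| m | u | f | Power in unilateral group |
|---|---|---|---|
| 0% | 165 | 0% | 46.5% |
| 5% | 156.75 (157) | 8.25/343.25 = 2.4% | 44.6% |
| 10% | 148.5 (148) | 16.5/351.5 = 4.7% | 42.7% |
| 20% | 132 | 33/368 = 9.0% | 38.8% |
| 30% | 115.5 (115) | 49.5/384.5 = 12.9% | 34.7% |

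Worked line for m = 30%: 9.4 × √(2/57.75) = 1.749; 2.74/1.749 = 1.566; 1.566 − 1.96 = −0.394; Φ = 0.347.

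The word match puts no bilateral case into the unilateral group. If miscoding is unrelated to arm and to treatment response, the estimate in the unilateral group loses precision but is not biased by this rule. The dilution falls on the comparison with the bilateral group.

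**The case against.** The strongest reply is that 9.6 and 9.11 can both be met by a film between randomization and first dose, and that 9.11 asks for closeness. That stands. A reader might infer that the subgroup is post-treatment as a settled matter, or that the film is usually taken after the first dose. The documents support neither: they give no film dates or imaging frequency, and an admission film is accepted when it is the only one. What remains is that 9.11 on its own sets no end to the window.

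It can also be said that treatment is unlikely to change laterality on a film near randomization. Section 2.4.3 places reactivation after the onset of respiratory failure, and Section 4.4 puts plasma reactivation before day 5 at under 8%. This is fair for a near film and says little about a late one. Site staff other than pharmacists are blinded (Section 6.4), so coding that differs by arm through knowledge of assignment is unlikely.

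Two other strong readings fail. Laterality is not itself an eligibility feature, since either pattern qualifies. A code of no infiltrates does not by itself contradict entry: 4.1.1 accepts any chest imaging, while 9.11 classifies a radiograph, so a later or less sensitive image may show nothing.

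Finally, Section 4.1.1 says that training clinicians does not make them apply the bilateral criterion accurately. A word rule is at least reproducible, and site PI reading will also be imperfect. That limits what any fix can achieve, but it does not justify leaving an effusion or a negated phrase coded as bilateral infiltrates without review.

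**Conclusion.** The point holds as a conflict in timing rules and a one-directional coding weakness. The variable can be post-treatment and can misclassify unilateral cases; the documents do not show that it is or does, or how often. Under the assumed 33% unilateral share and 5% to 30% miscoding, the labelled unilateral group falls from 165 to between 157 and about 115, its power for 2.74 days falls from about 46% to between 45% and 35%, and the contrast with the bilateral group shrinks by about 2% to 13%. The 67% is a rough proxy for the bilateral share, and the miscoding range comes from no source. The subgroup is underpowered even with perfect coding. SAP Section 4 reports that enrollment was closed after the last DSMB meeting, without giving the number enrolled, so the real counts may be lower than those based on 500.

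The consequence is confined to one subgroup listed in the protocol. The primary, key secondary, mortality and safety analyses do not depend on laterality. SAP Section 11 omits the subgroup and places subgroup work in a companion document not available here, so its status is unresolved.

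**What to change.** - In 9.11, classify infiltrates from the last chest image obtained before randomization, or at the latest before the first dose. Give 9.6 the same rule.
- Replace the word match: assign bilateral only when the report describes infiltrates or opacities in both lungs. Otherwise the blinded site PI classifies.
- Keep the no-infiltrates code, but flag each such case for eligibility review so that a late or less sensitive film can be told apart from an ineligible participant.
- Record the date and time of the film used, so that any classification from a film after the first dose can be identified.
- State in the SAP whether the unilateral-infiltrate subgroup is retained. If it is dropped, record that in SAP Section 12.

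With enrollment closed, this means re-abstracting existing reports, plus some added reading by site PIs. Protocol Section 5.4 already plans a review of medical records, so the extra work is modest. No new imaging is needed.
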